### 5.9.3 Suggested Management of Interstitial Lung Disease

Although quite rare, interstitial lung disease (ILD) is a class effect of EGFR TKIs and can be life threatening. Therefore, patients should be monitored closely for symptoms consistent with ILD, such as new onset dyspnea without an obvious cause. Chest CT should be obtained to look for interstitial fibrotic changes if ILD is suspected. In the event that ILD is suspected, drug treatment should be discontinued and the patient should receive appropriate medical management and supportive care. Although there is no established treatment, systemic corticosteroids are often administered. BIBW 2992 should not be restarted in those patients suspected of having drug-related ILD and the subject should be removed from the study.

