### 5.10 Duration of Therapy

Duration of therapy will depend on individual response, evidence of disease progression and tolerance. In the absence of treatment delays due to adverse events, treatment may be given continuously until one of the following criteria applies:

- Disease progression by RECIST criteria (see Section 8.3) Note that if a patient has progression by RECIST but is still deriving clinical benefit and there is not likely to be harm from continuing treatment, patients may continue therapy until no longer clinically benefitting, after discussion with and approval by the Sponsor, [name].
- Retreatment criteria are not met within the specified time frame (see Section 5.5)
- Intercurrent illness that prevents further administration of treatment,
- Unacceptable adverse event(s),
- Participant decides to withdraw from the study, or
- General or specific changes in the participant's condition render the participant unacceptable for further treatment in the opinion of the treating investigator.
- Death
- Lost to follow-up

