## 8. EFFICACY ASSESSMENT

Although response is not the primary endpoint of this trial, participants with measurable and/or non-measurable disease will be assessed by RECIST version 1.1 criteria. For the purposes of this study, participants should be reevaluated every 8 weeks. In addition to a baseline scan, confirmatory scans should also be obtained 4-8 weeks following initial documentation of an objective response.

Response and progression will be evaluated in this study using the criteria proposed by the Response Evaluation Criteria in Solid Tumors (RECIST) guideline. Changes in the diameter (unidimensional measurement) of the tumor lesions are used in the RECIST criteria.

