### 8.1 Definition of Terms

#### 8.1.1 Evaluable Cohorts

Evaluable for toxicity. All participants who receive at least one dose of study treatment will be evaluable for toxicity from the time of their first treatment.

CONFIDENTIAL

This document is confidential. Do not disclose or use except as authorized.

Evaluable for objective response. Only those participants who have measurable disease present at baseline, have received at least one cycle of therapy, and have had their disease re-evaluated will be considered evaluable for response. These participants will have their response classified according to the definitions stated below. (Note: Participants who exhibit objective disease progression or die prior to the end of cycle 1 will also be considered evaluable.)

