**Table 3. Evaluation of Best Overall Response For Patients with Measurable Disease**

Target Lesions	Non-Target Lesions	New Lesions	Overall Response	Best Overall Response for when Confirmation is Required:
CR	CR	No	CR	≥4 wks confirmation
CR	Non-CR/Non-PD	No	PR	
CR	Not evaluated	No	PR	
PR	Non-CR/Non-PD/Not evaluated	No	PR	
SD	Non-CR/Non-PD/Not evaluated	No	SD	Documented at least once ≥4 wks from baseline
PD	Any	Yes or No	PD	No prior SD, PR or CR
Any	PD*	Yes or No	PD	
Any	Any	Yes	PD	

\* In exceptional circumstances, unequivocal progression in non-target lesions may be accepted as disease progression.

**Note:** Participants with a global deterioration of health status requiring discontinuation of treatment without objective evidence of disease progression at that time should be reported as "*symptomatic deterioration*". Every effort should be made to document the objective progression even after discontinuation of treatment.

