## 9. STUDY CALENDAR

Screening evaluations are to be conducted within 4 weeks prior to start of protocol therapy, unless otherwise noted. All assessments must be performed prior to administration of any study medication. All study assessments and medications should be administered within  $\pm$  3 days of the protocol-specified date, unless otherwise noted.

	Screening	Treatment Period ( $\pm$ 3 days)											Off-Study a	Survival Follow-up
Cycleb (C) and Day (D)	Day-28 to 0	C1 D1	C1 D8	C1 D1 5	C2 D1	C3 D1	C4 D1	C5 D1	C6 D1	C7 D1	C8+			
Informed consent and confirmation of eligibility	X													
Medical History, Vitals, Physical Exam and AEs c	X	X	X	X	X	X	X	X	X	X	X d	X		
Concomitant medications	X	X	X	X	X	X	X	X	X	X	X d	X		
Laboratory testing e	X	X	X	X	X	X	X	X	X	X	X d	X		
ECG	X													
Tumor assessment (RECIST) g	X					X		X			X	X g	X	
Circulating Tumor Cell (CTC) Assay h		X	X	X	X	X	X	X		X	X h	X		
Repeat Tumor Biopsy i												X		X i
Survival and subsequent therapy j														X

- a Off-Study visit** – The off-study assessments will be performed when the subject meets criteria for study discontinuation (see Section 5.10).
- b Cycles** are 28 days long
- c Vitals** include temperature, blood pressure, respiratory rate, pulse, height, weight, performance status. **Medical history** should include recording all interim illnesses and assessment of **adverse events**.
- d After Completion of Cycle 8** visits for medical history, vitals, physical exam, assessment of adverse events, concomitant medications and laboratory evaluations need only be done every 2 months. These visits will correspond with the schedule for restaging scans (see below) and can be thought of as occurring after cycles 8, 10, 12, etc or can also be thought of as occurring at the beginning of cycles 9, 11, 13, etc.

test (if applicable). Studies to be done at the start of each cycle of treatment include CBC, LFTs, BUN, Cr, calcium, and electrolytes.

- f Tumor Measurement** – Baseline scans can be performed up to 28 days prior to start of treatment. Follow-up scans should be performed within 10 days of the start of cycles 3, 5, 7, 9, etc. This can also be thought of as following cycles 2, 4, 6, 8, etc.

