## 12.3 Data to Be Analyzed

Evaluable for the primary endpoint (acquisition of T790M): All patients who undergo a repeat biopsy will be evaluable for acquisition of T790M. If the results of this test are not interpretable due to technical failure of the assay, T790M will be assumed to be present (the more conservative assumption in terms of affecting the primary endpoint). Patients that do not undergo a repeat biopsy will not be included in the primary endpoint analysis.

Evaluable for toxicity. All participants who receive at least one dose of study treatment will be evaluable for toxicity from the time of their first treatment.

Evaluable for objective response. Only those participants who have measurable disease present at baseline, have received at least one cycle of therapy, and have had their disease re-evaluated will be considered evaluable for response. These participants will have their response classified according to the definitions stated below. (Note: Participants who exhibit objective disease progression or die prior to the end of cycle 1 will also be considered evaluable.)

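### The response rate leaves out treated patients who stop in cycle 1 without progression or death, or who are never re-scanned, and no rate over all treated patients with measurable disease is planned beside it

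*Combined protocol and SAP*

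**What the plan says.** Section 12.3 requires three things before a patient enters the response denominator: measurable disease at baseline, at least one cycle received, and a re-evaluation. In its words, patients who "have received at least one cycle of therapy, and have had their disease re-evaluated will be considered evaluable for response". One note widens the set: "Participants who exhibit objective disease progression or die prior to the end of cycle 1 will also be considered evaluable". Section 8.1.1 gives the same definition ("Only those participants who have measurable disease present at baseline, have received at least one cycle of therapy") and no second response set.

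Section 12.7 plans a RECIST response rate with 95% confidence intervals and names no other denominator or sensitivity analysis. The set of patients with at least one dose is defined in 8.1.1 and 12.3, but only for toxicity. Section 12.4 promises a summary of who was included in and excluded from the efficacy analyses.

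Section 8 schedules re-evaluation every 8 weeks, and the Study Calendar places the first follow-up scan around the start of cycle 3. Section 8 also states that "confirmatory scans should also be obtained 4-8 weeks following initial documentation of an objective response".

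**The concern.** Two of the three conditions are post-baseline events, so the denominator depends partly on how treatment went. Two groups of treated patients with measurable disease fall outside it:

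1. Patients who stop during cycle 1 without progression or death in that cycle. Section 5.10 provides for withdrawal ("Participant decides to withdraw from the study") and for unacceptable adverse events. Section 5.9.3 provides for removal when ILD is suspected ("BIBW 2992 should not be restarted in those patients suspected of having drug-related ILD and the subject should be removed from the study").
2. Patients who complete cycle 1 but stop, are lost or die with no re-scan.

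The rule also treats similar outcomes differently. A patient who dies unscanned in week 3 is counted as evaluable. One who dies unscanned in week 6, after cycle 1 but before the first scheduled scan, is not. Neither has a documented response, and the plan does not explain the difference.

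At stake is the first secondary objective, estimation of the response rate. If patients are excluded, the reported rate can exceed the rate among all treated patients with measurable disease. If only one denominator is pre-specified, any other rate added later would be chosen with the results known.

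**Working it through.** **The plan's own figures.** The documents state no response-rate assumption, precision or power for this trial, so there is nothing to reproduce on this point. The only power figure is the 86% in 12.2 for T790M (18 biopsies, 50% versus 20%, one-sided 0.05). Rejecting at 5 or fewer of 18 gives an exact alpha of 0.048 and power of 0.867, which agrees. That analysis does not use the response set.

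**Direction of the shift.** A group 2 patient has no post-baseline measurement and cannot be a documented responder. A group 1 patient would need a response on a scan after stopping and a confirmatory scan 4-8 weeks later. That is possible but unlikely, and excluding such a patient would lower the reported rate.

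**Inputs.** The number treated, n, is 24 (section 12.1) or 20 (section 1.1, which differs). The illustrative response level is the 63% first-line rate reported for the earlier phase II trial in 2.1.3. Assumptions, not in the documents: all treated patients have measurable disease, and the number of excluded non-responders, k, runs from 0 to 3.

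**Formula.** With r responders among n patients, excluding k non-responders changes the rate from r/n to r/(n − k). The shift is (r/n) × k/(n − k). Intervals are exact (Clopper-Pearson).

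**n = 24, r = 15** (63% of 24 = 15.1):

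| Excluded | Reported rate | Exact 95% CI | Shift (points) |
|---|---|---|---|
| none | 15/24 = 62.5% | 40.6 to 81.2 | 0 |
| 1 non-responder | 15/23 = 65.2% | 42.7 to 83.6 | +2.7 |
| 2 non-responders | 15/22 = 68.2% | 45.1 to 86.1 | +5.7 |
| 3 non-responders | 15/21 = 71.4% | 47.8 to 88.7 | +8.9 |
| 1 responder | 14/23 = 60.9% | 38.5 to 80.3 | −1.6 |
| 1 responder and 1 non-responder | 14/22 = 63.6% | 40.7 to 82.8 | +1.1 |

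For k = 2, for example, the shift is 0.625 × 2/22 = 0.057.

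**n = 20** (63% of 20 = 12.6, so both neighbouring counts are shown). With 12 responders, 60.0% becomes 63.2%, 66.7% and 70.6% for k = 1 to 3 (+3.2, +6.7, +10.6). With 13 responders, 65.0% becomes 68.4%, 72.2% and 76.5% (+3.4, +7.2, +11.5).

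**Scale.** With no exclusions the interval is about 41 points wide at 15/24 and about 45 points at 12/20 (36.0 to 80.9). Every shift above is small beside that. Criterion 3.1.3 also admits patients with evaluable but not measurable disease. The true n may therefore be below 24, and for a given response rate each exclusion would then weigh slightly more.

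**The case against.** The strongest reply is that little is left to correct.

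- **Early failures are mostly counted.** The note in 12.3 already includes progression and death in cycle 1, the exclusions that would inflate the rate most.
- **The remaining groups look small.** Section 5.9.3 describes ILD as rare. Section 5.8.2 allows up to 28 days for toxicity to resolve, so removal for non-recovery would usually fall after cycle 1. Criterion 3.2.13 excludes a life expectancy under 12 weeks, beyond the first 8-week scan.
- **Later scans can recover patients.** The calendar states that "The off-study assessments will be performed when the subject meets criteria for study discontinuation", and its tumour-assessment row appears to include an off-study scan. Its survival follow-up note asks for scans every 8-12 weeks, where possible, after stopping without progression. After symptomatic deterioration, the note to Table 3 says "Every effort should be made to document the objective progression even after discontinuation of treatment".
- **Exclusions will be disclosed** under 12.4.
- **The alternative is imperfect.** Scoring unscanned patients as non-responders can understate response.

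All of this stands as a limit on size, but it does not close the gap. Later scans help patients who completed cycle 1. A patient with less than one cycle stays out even if scanned later, unless progression or death occurred before the end of cycle 1. The plan also does not say whether an interrupted cycle counts as one cycle. Section 12.4 commits to a summary of exclusions, not to a second rate. A reader could rebuild that rate only if exclusions were broken down by measurable disease and scan status, which 12.4 does not promise.

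**Conclusion.** The concern holds. The response denominator is conditioned on receiving a cycle and being re-evaluated, the exception covers only progression or death in cycle 1, and no rate over all treated patients with measurable disease is planned. If patients are excluded, the likely effect is upward: about 3 points for one non-responder and about 9 for three, assuming 15 responders among 24 treated patients with measurable disease. With no exclusions there is no shift, and an excluded responder would move the rate down.

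The consequence is limited. Response rate is a secondary estimate in a pilot study, with no test, threshold or planned comparison. The T790M primary endpoint, PFS and OS are unaffected. This is a worthwhile, inexpensive improvement in reporting and does not threaten the trial's main conclusion.

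**What to change.** In 8.1.1, 12.3 and 12.7, pre-specify the response rate among all patients with measurable disease at baseline who received at least one dose. Classify every patient with a post-baseline scan by those scans, including patients who stopped in cycle 1. Count patients with no post-baseline assessment as non-responders. Report this rate with an exact 95% confidence interval beside the existing rate, which is kept and labelled response-evaluable.

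The cost is wording in three sections, with no new data or visits. The added rate may be slightly lower than the existing one, and it may understate response if an unscanned patient had in fact responded. Showing both rates lets the reader judge.

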## 12.4 Patient Disposition

CONFIDENTIAL

This document is confidential. Do not disclose or use except as authorized.

A detailed description of patient disposition will be provided. It will include:

- A definition of patient enrollment
- A summary of data regarding patient discontinuation of study treatment
- A summary of data regarding patient inclusion and exclusion in efficacy and safety analyses

## **12.5 Patient Characteristics**

Patient characteristics will include a summary of the following:

- Patient demographics
- Baseline disease characteristics
- Baseline tumor molecular characteristics
- Significant medical history and co-morbidities
- Concomitant therapies
- Other characteristics as appropriate

## **12.6 Safety of Treatment**

A summary of the adverse events and their attributed relatedness to treatment will be provided.

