The Adverse Events (AEs) observed to date in Phase I and Phase II trials are consistent with those reported for other EGFR tyrosine kinase inhibitors (dose dependent diarrhea and skin-related adverse events including rash and acne). Other AEs were in the expected range for patients with advanced cancer disease (ref investigator's brochure). In the BIBW 2992 Phase I monotherapy trials, the most frequent drug-related adverse events were associated with gastrointestinal disorders (diarrhea, nausea, vomiting, stomatitis), skin and subcutaneous tissue disorders (rash, dry skin, pruritus, acneiform rash, and acne), general disorders and administration site conditions (fatigue, mucosal inflammation), respiratory disorders (epistaxis, typically grade 1), and metabolism and nutritional disorders (anorexia, dehydration).

Diarrhea is the single most often reported gastrointestinal AE. An increased incidence of diarrhea grade 3 has been observed in phase II monotherapy trials (starting dose of 50 mg qd). Prompt and proactive management of diarrhea together with timely treatment pause and dose reduction is crucial to reduce the severity of diarrhea and its potential complications such as dehydration leading to serum electrolyte changes (hyponatraemia, hypokalaemia and hypomagnesaemia) and/or renal impairment.

Nausea and vomiting are the other commonly reported gastrointestinal adverse events and can be generally managed successfully with the use of antiemetics.

Skin related adverse events present in a number of forms, i.e., rash (including erythematous, maculopapular, papular, etc.), acne, dermatitis acneiform, dry skin, skin reaction and pruritis. Folliculitis as well as nail changes (including paronychia) are other reported manifestations of skin-related adverse events with BIBW 2992. Early and adequate management of skin-related adverse events can reduce the frequency and the severity of them.

Further AEs included oral discomfort (stomatitis, mouth ulceration, oral pain, dry mouth, soft tissue disorder) and mucosal inflammation. Conjunctivitis and rhinorrhea as a result of inflammation in the mucosal membranes have been reported. Mucosal and skin dryness can lead to epistaxis, which has to date been observed at CTCAE Grade 1. Anorexia, fatigue and asthenia are also frequently observed.

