### **6.1.3 Laboratory Examinations**

Laboratory examinations to be performed during screening include hemoglobin, white blood cell count including neutrophil count (sum of polysegmented granulocytes and band forms), platelets, bilirubin, alkaline phosphatase, ALT, AST, blood urea nitrogen (BUN), creatinine, calcium, electrolytes (sodium, potassium), and a urine pregnancy test (for women of child-bearing age).

Laboratory examinations are to be performed at the start of each cycle of treatment, on days 8 and 15 of cycle 1, and at the time of study discontinuation include hemoglobin, white blood cell count including neutrophil count (sum of polysegmented granulocytes and band forms), platelets, bilirubin, alkaline phosphatase, ALT, AST, blood urea nitrogen (BUN), creatinine, calcium and electrolytes (sodium, potassium).

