## **6.2 Definition of Terms**

### **6.2.1 Adverse Event (AE)**

An adverse event (AE) is any undesirable sign, symptom or medical condition or experience that develops or worsens in severity after signing informed consent or any procedure specified in the protocol, even if the event is not considered to be related to the study.

Abnormal laboratory values or diagnostic test results constitute adverse events only if they induce clinical signs or symptoms or require treatment or further diagnostic tests.

CONFIDENTIAL

This document is confidential. Do not disclose or use except as authorized.

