#### **4.10.4 Treatment Form(s)**

**Purpose** - Records the following information related to the time the participant receives protocol treatment:

- Participant, Protocol information
- Protocol treatment and supportive therapy per treatment cycle
- Protocol specific laboratory values per treatment cycle
- All medications other than protocol chemotherapy agents used to treat concomitant diagnoses, if applicable

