## **6.0 SAFETY ASSESSMENTS AND TOXICITY MONITORING**

All participants receiving investigational agents will be evaluated for safety. The safety parameters include all laboratory tests and hematological abnormalities, physical examination findings, and spontaneous reports of adverse events reported to the investigator by participants. All toxicities encountered during the study will be evaluated according to the NCI criteria specified in the protocol and recorded prior to each course of therapy. Life-threatening toxicities should be reported immediately to the Protocol Chair and Institutional Review Board (IRB).

Additional safety assessments and toxicity monitoring will be outlined in the protocol.

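### Section 12.6 summarises only adverse events, so collected laboratory changes that fall outside the 6.2.1 definition have no place in the planned safety results

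*Combined protocol and SAP*

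**What the plan says.** Section 12.6 is a single sentence: "A summary of the adverse events and their attributed relatedness to treatment will be provided". The rest of section 12 covers the T790M endpoint, disposition, patient characteristics, response, survival, biopsy complications and circulating tumor cells. None of it summarises laboratory values.

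Section 6.2.1 decides which laboratory findings reach that summary: "Abnormal laboratory values or diagnostic test results constitute adverse events only if they induce clinical signs or symptoms or require treatment or further diagnostic tests".

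Elsewhere the plan treats laboratory data as safety data:

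- Section 2.1.3 names, as potential complications of diarrhea, "dehydration leading to serum electrolyte changes (hyponatraemia, hypokalaemia and hypomagnesaemia) and/or renal impairment". Section 2.1.2 lists the kidney among the target organs in rats.
- Section 6.1.3 sets the schedule: "Laboratory examinations are to be performed at the start of each cycle of treatment, on days 8 and 15 of cycle 1", and again at discontinuation. The panel includes blood counts, liver tests, BUN, creatinine, calcium, sodium and potassium. Section 9 relaxes the schedule to every 2 months after cycle 8.
- Section 6.1 includes laboratory tests among the safety measurements. Appendix 3, section 6.0 says: "The safety parameters include all laboratory tests and hematological abnormalities".
- Appendix 3, section 4.10.4 has the Treatment Form capture "Protocol specific laboratory values per treatment cycle".

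Table 2 in section 5.5, in its column for adverse event type and grade, lists Grade 2 or higher worsening of renal function measured by serum creatinine. The conditions of 6.2.1 are not repeated there.

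**The concern.** The plan names a renal and electrolyte risk, schedules the tests that would detect most of it and stores the results. It then reports safety through a definition that can leave some of those results out. The filter works in one direction: 6.2.1 can remove a laboratory abnormality from the adverse event count but cannot add one.

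The count also depends on local behaviour. If one site orders an extra test for a raised creatinine and another waits for the next scheduled draw, the same value is an adverse event at the first and possibly not at the second. The mismatch between Table 2 and 6.2.1 adds to this. A site working from Table 2 would record a Grade 2 creatinine rise as an adverse event, while a site working from 6.2.1 might not. The adverse event table could then disagree with the record of holds and dose reductions.

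**Working it through.** The plan gives no figure on this point. Its only power figure concerns T790M and is not involved. The check is therefore a reading of the sections against each other, followed by an illustration on stated assumptions.

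**Step 1. Which laboratory changes reach the 12.6 summary?**

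| Laboratory change | Adverse event under 6.2.1? | In the 12.6 summary? |
|---|---|---|
| Causes signs or symptoms | Yes | Yes |
| No symptoms, but treated (e.g. electrolyte replacement) | Yes | Yes |
| No symptoms, but leads to further tests | Yes | Yes |
| None of these; seen again at the next scheduled draw | No | No |
| Grade 2 or higher creatinine-based worsening, drug held under Table 2, nothing else done | Unclear | Unclear |

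The fourth row is the gap. The fifth is an inconsistency: Table 2 calls the change an adverse event type, whereas under 6.2.1 the answer depends on whether a hold counts as treatment and whether repeat creatinine counts as a further test.

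**Step 2. Does another section fill the gap?** Section 6.3 records adverse events detected by laboratory test, but the finding must first be an adverse event. Appendix 3, section 4.10.4 stores the values without planning an analysis. Under section 10.2 the monitoring committee receives laboratory values on request. None of these puts the fourth row into a planned result.

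**Step 3. Direction.** Let p be the proportion of patients with a graded change and f the share of those meeting none of the 6.2.1 conditions. The reported proportion is p × (1 − f), which cannot exceed p.

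**Step 4. Size, on assumptions only.** The documents give neither p nor f. Take p from 5% to 30% and f from 25% to 75%. Expected patients missing = N × p × f.

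| N | Low end | High end |
|---|---|---|
| 24 (section 12.1) | 24 × 0.05 × 0.25 = 0.3 | 24 × 0.30 × 0.75 = 5.4 |
| 20 (section 1.1) | 20 × 0.05 × 0.25 = 0.25 | 20 × 0.30 × 0.75 = 4.5 |

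Both N are shown because the two sections disagree. As one case within the range, p = 20% of 24 gives 4.8 patients with a change. With f = 25% the table would show 0.20 × 0.75 = 15%; with f = 75% it would show 0.20 × 0.25 = 5%.

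The high end is unlikely for Grade 2 or higher creatinine worsening. Table 2 requires action there, so f should be small if sites record that action as an adverse event.

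**Step 5. What the collected values can show.** Eight cycles of 28 days are 224 days, about 7.4 months. Section 12.1 expects about 10 months on therapy, so a typical patient would have sparser sampling late in treatment. Section 6.1.3 specifies the electrolytes as sodium and potassium. Magnesium is not listed, although hypomagnesaemia is a named risk.

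**The case against.** The case against has real force in four places.

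- **Asymptomatic findings are not excluded as a class.** A reader might infer from 6.2.1 that they are. They are not: its conditions are alternatives, and an asymptomatic value that is treated or worked up is an adverse event. Only the remainder drops out. This stands and sets the limits of the point.
- **Table 2 already treats creatinine worsening as an adverse event.** Its notes require a hold until recovery, which for creatinine can be shown only by retesting, and section 6.3 records action taken with the drug. A reader might infer that patients dose-reduced for renal function will vanish from the safety table. The documents do not support that. They support only that Table 2 and 6.2.1 do not say the same thing.
- **The named risk is seldom silent.** Section 2.1.3 describes it as following diarrhea and dehydration, and section 5.9.1 recommends electrolyte replacement for Grade 2 and 3 diarrhea. Changes treated in that way count. This narrows the gap without closing it: scheduled draws also find changes unaccompanied by treated diarrhea.
- **Drug safety is not a listed objective.** This is a single-arm pilot whose only safety objective concerns repeat biopsies, and nothing bars tabulating the values later. That limits the seriousness. However, a later decision to tabulate would be discretionary and made with the data in hand.

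**Conclusion.** The point holds in limited form. Section 12.6 plans no summary of the collected laboratory values, and 6.2.1 leaves out graded changes with no symptoms, no treatment and no further test. Those changes would not appear in the safety results, so reported laboratory toxicity may be understated. Separately, Table 2 and 6.2.1 must be reconciled so that sites record creatinine-based renal worsening in the same way.

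The size cannot be computed from the documents. The range of 0.3 to 5.4 of 24 patients rests wholly on the assumed p and f and shows scale only. A reader might go further and conclude that a known harm is being under-reported. The documents show only that the plan permits this, not that it happens.

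The primary endpoint, sample size and power are unaffected. This is a cheap improvement to the safety report, not a flaw in the trial's main result.

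**What to change.** Add a paragraph to section 12.6 along these lines:

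> For creatinine, sodium, potassium, calcium, liver tests and blood counts, recorded values will be graded by CTCAE v4.0 regardless of symptoms or action taken. For all patients who received at least one dose, the worst on-treatment grade and the shift from baseline grade will be tabulated, with the number and percentage reaching Grade 2 or higher and Grade 3 or higher. Holds and dose reductions made for renal function will be listed alongside.

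Reconcile Table 2 with 6.2.1 and state the agreed recording rule once. Which text governs is for the sponsor and investigators to decide.

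State two limitations with the table: tests are every 2 months after cycle 8, and magnesium is not a listed test, so hypomagnesaemia cannot be shown. Confirm that the case report forms hold the day 8, day 15 and discontinuation values as well as those at cycle start.

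The cost is one paragraph, one table and a short listing from values already collected, with no new tests or visits. The safety profile may look slightly less favourable.
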